## PROTOCOL SUMMARY

Title:	Extension Protocol for Patients Previously Treated in Avapritinib Clinical Trials
Centers:	Multiple study centers worldwide that were previously active on avapritinib clinical trials.
Introduction and Rationale:	
Gastrointestinal stromal tumors (GIST) are the most common mesenchymal tumors occurring in the gastrointestinal (GI) tract, representing approximately 0.1–3.0% of all GI malignancies. Approximately 90% of patients with GIST have a tumor that is dependent on a mutation in either V-Kit Hardy-Zuckerman 4 feline sarcoma viral oncogene homolog (KIT) (75–80%) or the highly related protein platelet-derived growth factor receptor alpha (PDGFRA) (10–15%), most commonly a substitution of valine for aspartic acid at amino acid 842 (D842V) in exon 18. On a molecular level, the most common sites for mutations in KIT at the time of diagnosis are exon 11 (60–70%) and exon 9 (5–15%) with exon 17 mutations being identified in approximately 1% of patients. Disease progression during treatment with a tyrosine kinase inhibitor (TKI) is associated with new mutations in KIT, with an increasing prevalence of mutations in exon 17.
 
Avapritinib (also known as BLU-285) has demonstrated potent and selective activity against KIT exon 17 and PDGFRA exon 18 mutants in pre-clinical studies. Avapritinib has been shown to be tolerable at active doses in toxicology and safety pharmacology studies. In the ongoing Phase 1 GIST trial, clinical activity was also observed in a broad range disease driving mutations.
 
Avapritinib is now approved in the US for the treatment of adult patients with unresectable or metastatic GIST harboring a platelet-derived growth factor receptor alpha (PDGFRA) exon 18 mutation, including PDGFRA D842V mutations. Avapritinib is also approved in the EU for the treatment of adult patients with unresectable or metastatic GIST harboring a platelet-derived growth factor receptor alpha (PDGFRA) D842V mutations.

Number of Patients:	Approximately 5 patients may be treated in this extension study.

Objectives:	
The objectives of the study are:
 

• To provide long term safety data for GIST patients who are deriving clinical benefit from avapritinib on an existing avapritinib clinical trial To further characterize the rate of SAEs and AESIs of avapritinib.

Study Design:	
This is an open-label extension study to provide long term safety data for GIST patients who are deriving clinical benefit from avapritinib upon the completion of avapritinib clinical trials.

Duration of Patient Participation:	
The patient will remain on treatment and safety data will be collected as long as clinically appropriate according to the judgment of the Investigator.

Duration of Study:	
The study is anticipated to last 24 months, or when the last patient discontinues from the study.

Target Population:	
Patients who:
 

• Have histologically confirmed metastatic or unresectable GIST

• Have received prior treatment with avapritinib in a clinical trial and require continued therapy

• Are free of disease progression since receiving avapritinib

• Have adequate organ function

Dosage and Administration:	
Avapritinib will be administered orally (PO) at the dose received by the patient on the prior avapritinib protocol in continuous 28-day cycles. Dosing modifications for avapritinib-related toxicity is recommended; modification guidelines are provided in the protocol.

Efficacy Evaluations:	
Disease responses as assessed by Investigator according to local standard of care.

Safety Evaluations:	
General safety will be assessed by the monitoring and recording of all serious adverse events (SAEs), and adverse events of special interest (AESI) including cognitive effects and intracranial bleeding; regular monitoring of hematology and blood chemistry, regular measurement of vital signs and the performance of physical examinations and other safety assessments in accordance with standard of care.

Safety Analysis:	
Serious Adverse events (SAEs) will be graded according to the National Cancer Institute (NCI) Common Terminology Criteria

for Adverse Events (CTCAE) version 5. The proportion of patients who reported SAEs and AESIs will be collected and summarized for all patients who receive at least one dose of avapritinib.

Summary of SAE and AESIs will also be provided by Medical Dictionary for Regulatory Activities (MedDRA) system organ class (SOC) and preferred term (PT). Summary statistics will be provided for duration of avapritinib treatment. Dose discontinuation and reasons for dose discontinuation will also be reported.

**Efficacy Analysis:** Investigators will monitor response to treatment according to local standard of care. Response to treatment will not be collected.

## LIST OF ABBREVIATIONS

Abbreviation	Definition
AE	Adverse event
AESI	Adverse event of Special Interest
CTCAE	Common Terminology Criteria for Adverse Events
CYP	Cytochrome P450
CRF	Case report form
CRO	Clinical Research Organization
GI	Gastrointestinal
GIST	Gastrointestinal stromal tumor
IB	Investigator's Brochure
IEC	Independent Ethics Committee
KIT	V-kit Hardy-Zuckerman 4 feline sarcoma viral oncogene homolog
NCI	National Cancer Institute
ORR	Overall response rate
PDGFR $\alpha$	Platelet-derived growth factor receptor alpha
PFS	Progression-free survival
PO	Orally
PRO	Patient reported outcome
QD	Once daily
SAE	Serious Adverse Event
TKI	Tyrosine kinase inhibitor

## 1 BACKGROUND AND RATIONALE

### 1.1 Background

#### 1.1.1 *Gastrointestinal Stromal Tumor*

Gastrointestinal stromal tumors (GIST) is a rare sarcoma that arises from the interstitial cells of Cajal or their stem cell precursors. They are the most common mesenchymal tumors occurring in the gastrointestinal (GI) tract, representing approximately 0.1% - 3.0% of all GI malignancies (Miettinen and Lasota, 2006; Rammohan et al, 2013). GIST is most commonly diagnosed between the ages of 50 and 80 years, with a slight predilection for males (Nilsson et al, 2005).

Gastrointestinal stromal tumors may develop at any point along the GI tract, with the stomach (60%) and small intestine (30%) being the most common locations; the remaining 10% of GIST arise from the esophagus, colon, rectum, or the mesentery (Nilsson et al, 2005). GIST most commonly presents with GI bleeding, with obstruction or acute tumor rupture occurring more rarely (Rammohan et al, 2013). Slightly fewer than half of patients with GIST present with high-risk characteristics, such as large size, local infiltration, and/or metastasis (Goettsch et al, 2005; Nilsson et al, 2005). GIST typically progresses by local extension from its site of origin, intra-peritoneal spread, and metastases to the hepatic parenchyma. Metastases to lymph nodes are rare.

Surgery is the primary treatment for patients with resectable or potentially resectable GIST with the goal being to obtain histologically negative margins. GIST is not considered sensitive to either systemic cytotoxic chemotherapy or radiation therapy.

#### *Molecular Pathology of GIST*

Approximately 90% of patients with newly diagnosed GIST have a tumor that is dependent on a mutation in either V-kit Hardy-Zuckerman 4 feline sarcoma viral oncogene homolog (KIT) (75-80%) or the highly related protein platelet-derived growth factor receptor alpha (PDGFR $\alpha$ ) (10-15%) (Antonescu et al, 2005; Barnett and Heinrich, 2012; Corless et al, 2005). A majority of mutations in PDGFR $\alpha$  occur at amino acid 842, with the most common mutation at this site being a substitution of valine for aspartic acid (D842V). The remaining cases, denoted as KIT and PDGFR $\alpha$  wild-type, are due to other abnormalities such as succinate dehydrogenase deficiency (Nannini et al, 2013).

#### *KIT-mutated GIST*

On a molecular level, the most common sites for mutations in KIT at the time of diagnosis are exon 11 (60-70%) and exon 9 (5-15%) with exon 17 mutations being identified in approximately 1% of patients (Debiec-Rychter et al, 2006; Heinrich et al, 2008). Disease progression during treatment with a tyrosine kinase inhibitor (TKI) is most commonly due to the emergence of resistance mutations in KIT, including an increasing prevalence of those in exon 17, which are refractory to standard first and second line therapy, imatinib (Gleevec, 2016) and sunitinib (Sutent®, 2014). At the time

of progression on first-line TKI (imatinib) therapy, approximately 20-25% of patients had GIST harboring a mutation in exon 17 (Antonescu et al, 2005; Liegl et al, 2008; Wardelmann et al, 2006). No currently approved TKI selectively inhibits mutations in exon 17 of KIT.

Although imatinib is effective in many patients with GIST as first-line therapy, some patients do not respond and subsequent lines of therapy for those who respond are significantly less effective. Therapeutic failure appears linked to acquired resistance mutations, particularly those involving the ATP binding pocket (exons 13 and 14) and activation loop (exons 17 and 18) of KIT (Heinrich et al, 2008). Post-imatinib, ATP-binding pocket mutations and activation-loop mutations occur at a rate of ~30% and ~20%, respectively. Thirty-five percent of patients progress on imatinib without secondary mutations (mostly with KIT exon 9 mutations). The remainder of GIST patients who are unresponsive to imatinib harbor alterations in PDGFR $\alpha$  or succinate dehydrogenase (SDH). In KIT-mutant GIST, the response rate for patients with tumors bearing ATP-binding pocket mutations to sunitinib is low (ORR 11%) and responses rarely occur in the setting of activation-loop mutations (ORR 0%; Heinrich et al, 2008). Thus, patients failing imatinib due to either ATP-pocket or activation-loop mutations, represent an important medical need.

### ***PDGFR $\alpha$ -mutated GIST***

Gastrointestinal stromal tumors dependent on mutations in PDGFR $\alpha$  occur more frequently in the stomach, are more commonly resectable, have a somewhat more indolent clinical course than KIT-dependent GIST, and are less 2-deoxy-2-[fluorine-18]fluoro-D-glucose positron emission tomography (18FDG-PET) avid compared to GIST dependent on a mutation in KIT (Matro et al, 2014). Despite the more indolent course while localized, once metastatic, patients with GIST harboring the PDGFR $\alpha$  D842V mutation have an extremely poor prognosis and respond poorly to imatinib and other TKIs (Cassier et al, 2012; Goodman et al, 2007; Heinrich et al, 2008; Yoo et al, 2016).

In a retrospective study, Cassier et al identified 44 patients with PDGFR $\alpha$ -mutant GIST who had advanced disease from databases at 12 European institutions (N = 3,510 genotyped GIST patients) and an additional 16 patients with advanced,

PDGFR $\alpha$ -mutant GIST from the European Organisation for Research and Treatment of Cancer (EORTC) advanced GIST database (N = 465 genotyped GIST patients). Of 58 patients evaluable for efficacy post-imatinib, 32 patients (55%) had the

[figure not shown]
PDGFR $\alpha$  D842V mutation and the remainder had mutations in PDGFR $\alpha$  exon 4, 12, or 18 (non-D842V). The non-D842V patients had an overall response rate (ORR) of 36% with imatinib and median PFS >1 year. In contrast, patients with the D842V-mutation had no response (ORR = 0%). Median PFS with second-line treatment was short (2.1 months) and was not significantly different between imatinib, sunitinib, and other treatments. Similarly, in a small, retrospective Korean study (N=18) PDGFR $\alpha$ -mutant

GIST patients treated with imatinib reported a similar PDGFR $\alpha$  D842V prevalence (9/18; 50%) and poor outcome (median PFS 3.8 months and ORR 0% [0/5 evaluable patients]). Patients with the D842V substitution treated with sunitinib as second-line therapy reported median PFS 1.9 months and ORR 0% (Yoo et al, 2016). A recent multicenter, retrospective study of adult patients with locally advanced, metastatic, or recurrent PDGFR $\alpha$  D842 mutant GIST diagnosed between Jan 2000 and Jul 2016 who were treated with at least one TKI showed a median PFS consistent with the findings of other studies that have shown a median PFS of 3–5 months. Twenty-two patients were identified at 3 US academic institutions. One patient had a complete response to first-line imatinib following partial resection of the primary tumor and completed 1 year of treatment. No complete or partial responses were reported in patients receiving TKI treatment in the second-line or third-line setting. Median PFS across the first-, second- and third-line treatment groups was 5.6, 2.6, and 5.6 months, respectively (von Mehren et al, 2018). Avapritinib was first approved in the US on January 2020 for the treatment of adults with metastatic GIST harboring a PDGFRA exon 18 mutation and then received conditional approval in the EU in September 2020 as monotherapy for adult patients with unresectable or metastatic GIST harboring the PDGF D842V mutation. Avapritinib currently has an orphan drug designation in both the US and EU.

### **1.1.2 Avapritinib**

Avapritinib, a highly potent and selective oral kinase inhibitor, was designed to treat imatinib-resistant GIST by targeting KIT/PDGFR $\alpha$  activation loop mutants (exon 17/18). Avapritinib has potent activity on the KIT and PDGFR $\alpha$  activation loop mutants (exon 17/18), including the D842V mutation, with biochemical half-maximal inhibitory concentration (IC50) against all activation loop mutants of less than 2 nM (Figure 1). In addition, avapritinib has demonstrated considerable potency across a wide array of disease-relevant KIT mutants found in patients with GIST including those that appear as secondary mutants after imatinib treatment as well as the exon 11 mutants most commonly observed in imatinib-naïve GIST.

Avapritinib has demonstrated clinically important activity against GIST following 3 or more prior lines of therapy, and regardless of line of therapy in the setting of an exon 18 mutation in PDGFRA in the ongoing NAVIGATOR clinical study (Heinrich et al, 2018). Please refer to the avapritinib Investigator's Brochure (IB) for additional information.

**Figure 1: Biochemical Activity of Avapritinib Against Disease-relevant KIT Mutants**

Source: Evans EK et al. Sci Transl Med. 2017;9(414):eaao1690

### 1.1.3 Extension Study

This extension study is designed to provide long term safety data for GIST patients who are deriving clinical benefit from avapritinib on an existing avapritinib trial. GIST is a serious or immediately life-threatening condition, for which there are no standard treatment options available and continued treatment with avapritinib remains an effective treatment option.

This study is sponsored by Blueprint Medicines.

### 1.1.4 Extension Study Rationale

This extension study is designed to provide long term safety data for GIST patients who have been deriving clinical benefit from avapritinib treatment on an avapritinib trial that is has met its primary endpoints.

This extension study is designed to provide ongoing safety data on patients previously enrolled on avapritinib safety and efficacy studies, that have completed their planned analyses.

Overall, avapritinib has been well-tolerated in patients with GIST. Most AEs have been Grade 1 or Grade 2 in severity and consistent with the effects of KIT inhibition. Adverse events occurring in  $\geq 25\%$  of patients (regardless of relationship to avapritinib) included nausea (56%), fatigue (53%), periorbital edema (43%), vomiting (41%), peripheral edema (34%), anemia (31%), diarrhea (31%), cognitive effects (consisting of multiple similar AEs aggregated into a single category [30%]), increased lacrimation (30%), and decreased appetite (28%). Among 116 patients treated with avapritinib in the BLU-285-1101 study as of the 11 October 2017 data cut-off only 6 (5%) have discontinued treatment due to a treatment-related AE.

More detailed information about the known and expected benefits and risks and reasonably expected AEs of avapritinib may be found in the avapritinib IB.

## 2 STUDY OBJECTIVES

The objectives of the extension study are:

- To provide long term safety data for GIST patients who are deriving clinical benefit from avapritinib on an existing avapritinib clinical trial
- To further characterize the rate of SAEs and AESIs of avapritinib.

### 3 STUDY PLAN

#### 3.1 Study Design

This is an open-label extension study to provide long term safety data for GIST patients who are deriving clinical benefit from avapritinib on an existing clinical trial. Avapritinib will be administered orally (PO) in adult patients with unresectable GIST until such time that avapritinib becomes available through other mechanisms or the Sponsor chooses to discontinue the Study. Avapritinib will be administered once daily (QD) at the dose received by the patient on the prior avapritinib protocol in continuous 28-day cycles, with a maximum dose of 300 mg QD.

All study visits are intended to be conducted on an outpatient basis but may be conducted on an inpatient basis as needed. After provision of written informed consent, patients will be evaluated for eligibility during the screening period before avapritinib administration on Cycle 1 Day 1 (C1D1). A treatment cycle is 28 days in duration.

No minimum or maximum treatment duration has been set. Patients will be monitored at regular intervals for safety and for response to treatment, as per investigator assessed response. Patients may continue to receive avapritinib until precluded by toxicity, noncompliance, patient decision, physician decision, progressive disease, death, or closure of the study by the Sponsor.

All patients will have an End of Study evaluation with reason for discontinuation recorded.

### 4 POPULATION

#### 4.1 Number of Patients

Approximately 5 patients may be enrolled in this extension study.

#### 4.2 Selection of Patients

Patients must meet the inclusion and exclusion criteria to be enrolled in the trial. The Sponsor will consider inclusion of patients who do not meet the inclusion and exclusion criteria on a case by case basis following receipt of supporting information and rationale from the Investigator. Such exceptions may also require approval by the Independent Ethics Committee (IEC), as appropriate.

#### 4.3 Inclusion Criteria

Patients meeting the following criteria will be eligible for participation in the Study:

1. Patient has histologically confirmed metastatic or unresectable GIST as established by entry in a previous avapritinib clinical trial and has been receiving treatment with avapritinib on one of these trials.

2. Patient continues to receive clinical benefit from avapritinib treatment, as assessed by the investigator.
3. Patient or legal guardian, if permitted by local regulatory authorities, provides informed consent.

#### **4.4 Exclusion Criteria**

Patients meeting any of the following criteria will not be eligible for Study participation:

1. Patient requires therapy with a concomitant medication that is a strong inhibitor or strong inducer of cytochrome P450 (CYP) 3A4 (see [Section 5.4.1](#)).
2. Patient has a history of intracranial bleeding either prior to or during avapritinib treatment
3. Patients who have poor organ function, defined as Adverse Events of NCI CTCAE version 5.0 Grade 3 or higher at the time of enrollment must delay start of treatment until symptoms return to Grade 2 or baseline, or the start of treatment has been approved by the Sponsor.
4. Patients who have ongoing cognitive or mood effects Adverse Events of NCI CTCAE version 5.0 higher than Grade 1 must delay start of treatment until symptoms return to Grade 1 or baseline.
5. Women who are unwilling, if not postmenopausal or surgically sterile, to abstain from sexual intercourse or employ highly effective contraception from the time of enrollment and for at least 30 days after the last dose of avapritinib. Men who are unwilling, if not surgically sterile, to abstain from sexual intercourse or employ highly effective contraception from the time of first dose and for at least 90 days after the last dose of avapritinib. Refer to [Section 5.5.1](#) for acceptable methods of contraception.
6. Women who are pregnant, as documented by a serum beta human chorionic gonadotropin ( $\beta$ -hCG) pregnancy test consistent with pregnancy, obtained within 7 days before the enrollment. Females with  $\beta$ -hCG values that are within the range for pregnancy but are not pregnant (false-positives) may be enrolled with written consent of the Sponsor, after pregnancy has been ruled out. Females of non-childbearing potential (postmenopausal for more than 1 year; bilateral tubal ligation; bilateral oophorectomy; hysterectomy) do not require a serum  $\beta$ -hCG test.
7. Women who are breast feeding.
8. Patients with a known hypersensitivity to avapritinib or the excipients.

## 4.5 Patient Identification and Registration

Patients who are candidates for enrollment into this extension protocol will be evaluated for eligibility by the Investigator to ensure that the inclusion (see [Section 4.3](#)) and exclusion criteria (see [Section 4.4](#)) are met. Patients must be registered with the Sponsor (or Clinical Research Organization [CRO]) prior to approval for entry to the Study.

## 4.6 Patient Withdrawal Criteria

Patients have the right to withdraw from the Study at any time for any reason.

Patients must withdraw or be withdrawn from Study treatment for any of the following reasons:

- Withdrawal of consent;
- Pregnancy;
- Death.

Patients may withdraw or be withdrawn from Study treatment for any of the following reasons:

- AE;
- Disease progression;
- Protocol deviation;
- Investigator decision;
- Loss to follow-up.

When a patient discontinues Study drug, the primary reason(s) for discontinuation is to be recorded in the case report form (CRF). Following discontinuation of Study drug, all efforts will be made to complete and report the protocol-defined Study observations as completely as possible.

If a patient discontinues treatment because of an adverse event (AE), protocol-specified safety follow-up is to be performed, and the patient should remain under the supervision of the Investigator or designee until the condition has returned to baseline or stabilized.

## 5 STUDY CONDUCT

### 5.1 General Conduct

The schedule of assessments for the Study is provided in [Table 1](#).

The end of the Study is defined as the time that the last patient completes his/her last visit.

**Table 1: Schedule of Assessments**

Study Activities a	Screening	Treatment		EOT b
Cycle		C1	Every 3 months (+/- 15 days)	
Program Day	D0–28	D1	D1	
Informed consent	X			
Inclusion/Exclusion criteria	X			
Demographics	X			
Physical examination c	X	X	X	X
Vital signs d	X	X	X	X
ECOG status e	X			
Pregnancy ( $\beta$ -hCG) test f	X		X	
Hematology g	X	X	X	X
Serum chemistry h	X	X	X	X
Efficacy assessment i			Per Investigator discretion	
Avapritinib administration j		X		
SAE and AESI monitoring k		X		

Abbreviations: AE = adverse event; AESI = adverse event of special interest; ALP = alkaline phosphatase; ALT = alanine aminotransferase; aPTT = activated partial thromboplastin time; AST = aspartate aminotransferase;  $\beta$ -hCG = beta human chorionic gonadotropin; BUN = blood urea nitrogen; C = cycle, D = day, ECOG = Eastern Cooperative Oncology Group, EOT = end-of-treatment; GIST = gastrointestinal stromal tumor; Hgb = hemoglobin; INR = international normalized ratio; QD = once daily; SAE = serious adverse event; ULN = upper limit of normal.

a Additional safety tests may be performed whenever clinically indicated, at the Investigator's discretion. Whenever a test result is questionable, it should be repeated. Timing of procedures may be modified at Investigator discretion.

b At EOT, the reason for EAP discontinuation and last day of dosing should be recorded. This can be done by telephone if necessary.

c A complete physical examination including weight, evaluation of the skin, head and neck, lymph nodes, heart, lungs, breasts, abdomen, pelvis (if indicated based on symptoms), musculoskeletal system, neurologic system, and a basic assessment of mental status and mood will be performed at the Screening visit.

Subsequent physical examinations will focus on weight, signs of GIST, changes from previous physical examinations, neurologic, mental status, and mood examinations, and AEs.

d Vital signs include temperature, pulse, systolic/diastolic blood pressure, and weight.

e Refer to [Appendix 3](#) for ECOG performance status scoring.

f To be performed for women of child-bearing potential. A serum pregnancy test should be performed at baseline (within 7 days before the first dose of avapritinib). Serum or urine pregnancy test should be performed on D1 of every study visit, or more frequently if required by local requirements.

g Hematology parameters to be measured include hemoglobin, white blood cell count with differential count, and platelet count.

h Serum chemistry panel includes sodium, potassium, BUN or urea, bicarbonate (venous), creatinine, calcium, chloride, magnesium, phosphorus, albumin, AST, ALT, ALP, and total bilirubin (direct bilirubin if total bilirubin is > ULN).

i Disease response assessments should be performed per standard of care.

j Avapritinib will be administered QD in the morning at least 2 hours after and 1 hour before eating.

k SAEs, AESIs and concomitant medications are to be collected from the date of the informed consent signature through end of treatment. See [Section 9](#) for details of SAE/AESI.

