### **6.2.5 Adverse Events and Concomitant Medications**

Each patient must be carefully monitored for the development of any AEs throughout the study from the start of avapritinib administration (or from the time of signing informed consent, for SAEs) to 30 days after the last administration. In addition, SAEs that are assessed to be at least possibly related to Study treatment that occur > 30 days posttreatment are to be reported.

Adverse events will be recorded locally, but only SAEs will be reported to the sponsor or its designee. Complete details on AE and SAE monitoring are provided in [Section 8](#) and [Section 9](#), respectively.

Concomitant medications will be recorded from the time of signing informed consent to 30 days after the last dose.

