## 8 ADVERSE EVENTS

All patients will be monitored for adverse events throughout their participation in the Study. Serious AEs and adverse events of special interest (AESIs) will be recorded in the CRF from the time of first dose of avapritinib through 30 days after the last avapritinib dose. In addition, serious adverse events (SAEs) and AESIs that are assessed as related to avapritinib treatment and that occur > 30 days posttreatment will also be reported. All related SAEs and AESIs should be monitored until they are resolved, stabilized, have returned to pre-exposure baseline, determined to be due to another illness, or until a subsequent therapy is initiated.

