## **9.6 Pregnancy Reporting**

Pregnancy is neither an AE nor an SAE, unless a complication relating to the pregnancy occurs (eg, spontaneous abortion, which may qualify as an SAE).

Pregnancies and suspected pregnancies (including a positive pregnancy test regardless of age or disease state) of a female patient or partner of a male patient occurring while the patient is being treated with avapritinib, or within 30 days of the patient's last dose of avapritinib, are considered immediately reportable events. If a female partner of a male patient taking investigational product becomes pregnant, the male patient taking avapritinib should notify the Investigator, and the pregnant female partner should be advised to call her healthcare provider immediately. In pregnant female patients, avapritinib is to be discontinued immediately and the patient instructed to return any unused avapritinib to the Investigator. The pregnancy, suspected pregnancy, or positive pregnancy test must be reported immediately using the Pregnancy Report Form. The Investigator must follow up and document the course and outcome of all pregnancies even if the patient was discontinued from the Study or if the Study has finished. The female patient or partner of a male patient should receive any necessary counseling regarding the risks of continuing the pregnancy and the possible effects on the fetus. Monitoring should continue until conclusion of the pregnancy.

All outcomes of pregnancy must be reported by the Investigator to the Sponsor or Medical Monitor on a Pregnancy Outcome Report form within 30 days after he/she has gained knowledge of the delivery or elective abortion.

Any SAE that occurs during pregnancy must be recorded on the SAE report form (eg, maternal serious complications, spontaneous or therapeutic abortion, ectopic pregnancy, stillbirth, neonatal death, congenital anomaly, or birth defect) and reported within 24 hours in accordance with the procedure for reporting SAEs.

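### Safety capture runs to 30 days after the last dose, but no contact is required at or after day 30, so active ascertainment of that window is unscheduled

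*Combined protocol and SAP*

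**What the plan says.** Several obligations run past the last dose:

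- Section 8: SAEs and AESIs "will be recorded in the CRF from the time of first dose of avapritinib through 30 days after the last avapritinib dose". Events judged related to avapritinib are reported even later than that.
- Section 6.2.5: adverse events are monitored "to 30 days after the last administration". "Concomitant medications will be recorded from the time of signing informed consent to 30 days after the last dose".
- Section 9.6: pregnancies on treatment or within 30 days of the last dose "are considered immediately reportable events".

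The schedule stops earlier. Table 1 has four columns: screening, Cycle 1 Day 1, a three-monthly visit, and EOT. Footnote b says of the last: "At EOT, the reason for EAP discontinuation and last day of dosing should be recorded. This can be done by telephone if necessary". Nothing states how long after the last dose EOT takes place. Footnote k has SAEs, AESIs and concomitant medication collected only until treatment ends. The pregnancy-test row has no mark under EOT.

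Three further passages matter. Section 3.1 promises every patient an End of Study evaluation, gives it no timing, and names only the discontinuation reason as its content. Section 4.6 says that, for a patient who stops because of an adverse event, "protocol-specified safety follow-up is to be performed". Section 5.1 says: "The end of the Study is defined as the time that the last patient completes his/her last visit".

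**The concern.** A site works from the schedule table. If it follows Table 1 and footnote k as written, it can hold EOT at the last dose, stop collecting, and close the patient while the window in Section 8 has still to run.

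Section 9.3 gives the routes by which SAEs and AESIs are found: open questions to the patient, signs found at examinations, staff observation, and what the patient reports unprompted. After EOT the plan fixes no occasion for the first three. AESIs count at any grade and whatever the cause, so mild memory impairment or confusion qualifies, and a patient may not think to report it. The 24-hour SAE clock in Section 9.2 starts only once the investigator is aware of the event.

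Characterising the rate of SAEs and AESIs is a stated objective (Section 2). Incomplete ascertainment acts in one direction: it lowers the reported proportions or leaves them unchanged. A report of no events after stopping could not be told apart from a report in which nobody was asked. Section 10 treats these data as continuing the patients' earlier safety record, so a loss here carries into the wider avapritinib assessment.

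**Working it through.** The plan gives no figure to reproduce on this point. The number of patients is an expected roll-over count, and no hypothesis is tested. The check sets the windows against the contacts and then gives a scale.

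**1. Contacts that could cover the 30 days**

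| Contact | Source | Timing relative to last dose | Covers day 30? |
|---|---|---|---|
| EOT | Table 1, footnote b | none stated | only if the site chooses day 30 or later |
| End of Study evaluation | Section 3.1 | none stated; not in Table 1 | only if the site chooses day 30 or later |
| Safety follow-up | Section 4.6 | not defined; only after stopping for an adverse event | cannot be determined |

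Contacts required at or after day 30: 0.

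**2. Collection window.** Sections 6.2.5 and 8 say 30 days after the last dose. Table 1 footnote k says end of treatment. Both cannot hold, and the schedule follows the shorter one. Even if footnote k were kept, Section 9.6 would leave pregnancies reportable to day 30.

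**3. End of study.** If the last patient's last visit falls *d* days after the last dose, with *d* below 30, then 30 − *d* days of that patient's window remain when the study ends. The plan does not set *d*, so the remainder can be anything up to 30 days. This applies to the last patient only. For the others the gap is the missing follow-up contact.

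**4. Size of the uncovered time.** Inputs: n = 5 (Section 4.1) and a 30-day window (Section 8). Treatment duration T is an assumption: 24 months, taken from the anticipated study duration in the Protocol Summary, with 12 and 6 months as alternatives. One month is 365.25/12 days.

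- Total: 5 × 30 = 150 patient-days.
- Share of time at risk = 150 / [5 × (T + 30)].
- T = 24 months (730.5 days): 150/3802.5 = 3.9%.
- T = 12 months (365.25 days): 150/1976.25 = 7.6%.
- T = 6 months (182.6 days): 150/1063.1 = 14.1%.

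**5. Effect on the reported proportion.** The summary counts patients with an event. One patient whose only event falls in the window moves it from 0/5 (0%, exact 95% interval 0 to 52%) to 1/5 (20%, 0.5 to 72%).

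**6. Chance that it matters.** With an assumed per-patient risk p of an event in the window, the chance of at least one such patient among five is 1 − (1 − p)^5:

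- p = 1%: 4.9%
- p = 2%: 9.6%
- p = 5%: 22.6%
- p = 10%: 41.0%

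The documents give no value for p, so these figures only show the range.

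**The case against.** The best defence is that the plan does not stop looking after patients at EOT. Section 6.2.5 requires careful monitoring to day 30. Section 4.6 asks for every effort to complete observations after discontinuation, and for supervision of a patient who stopped for an adverse event until it settles. Related events are followed under Section 8, and known pregnancies are followed under Section 9.6 even after the study has finished. EOT and the End of Study evaluation are untimed, so a site may hold either at day 30. Section 6.5 limits data collection on purpose, and with about five patients the intervals for 0/5 and 1/5 largely overlap.

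Much of this stands. It means that the duty to monitor and report survives, and that the end-of-study definition does not cancel it. It does not supply a contact: nothing obliges a site to speak to the patient at day 30, and footnote k tells it to stop collecting sooner.

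A reader might infer several stronger things that the documents do not support:

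- *That the whole EOT visit may be a phone call.* The telephone sentence in footnote b follows the instruction to record the discontinuation reason and last dosing day, and most naturally covers only those. The EOT column also marks physical examination, vital signs, hematology and chemistry.
- *That events would surface only if patients volunteer them.* The monitoring duties above say otherwise.
- *That the 30 days are a period of raised risk.* No figure in the documents shows this. The nearest is 6 of 116 patients (5%) in the earlier study who stopped for a treatment-related adverse event. Patients may also leave because drug becomes available elsewhere or the study closes.
- *That SAEs and AESIs are all the study reports.* Treatment duration and discontinuation reasons are summarised too.

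**Conclusion.** The point holds as a gap in scheduled active ascertainment. The plan counts events to 30 days after the last dose, requires no contact at or after day 30, and contradicts its own window in footnote k. A site that follows Table 1 exactly can lose events that bear on a stated objective, and the loss can only lower the reported proportions.

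The size is modest: 150 patient-days, or 3.9% of time at risk under 24 months of treatment per patient, rising to 7.6% and 14.1% at 12 and 6 months. These shares rest on n = 5 and on assumed durations. The change from 0/5 to 1/5 requires a patient with no SAE or AESI earlier in the study. No formal decision rests on the proportion. The case for acting is that the objective is safety, the error has a known direction, and the remedy is cheap.

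**What to change.** 1. Reconcile Table 1 footnote k with Sections 6.2.5 and 8, so that one collection window applies throughout.
2. Add one column to Table 1 after EOT: a contact, by telephone if convenient, timed to the end of the retained window. It should record SAEs, AESIs, concomitant medication and, where applicable, pregnancy status. If the retained window is shorter than 30 days, pregnancy status still needs a contact that satisfies Section 9.6.
3. Cite that contact in Section 4.6 as the safety follow-up, and state how the Section 3.1 End of Study evaluation relates to it.
4. Define end of study in Section 5.1 as the last patient completing that contact.
5. In footnote b, say that the telephone option covers the discontinuation reason and last dosing day only.

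The cost is protocol wording, about five calls (one per patient), and a study end up to about 30 days later.
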